A Randomized Controlled Trial of use versus non-use of bladder catheterization in elective cesarean delivery

Investigators

[name], MD FRCP Obstetrics and Gynecology - Principal Investigator

[name], MD, PhD, FRCSC Obstetrics and Gynecology, Gynecologic Oncology - Principal Investigator

[name], PhD - Department of Obstetrics and Gynecology - Co-investigator

[name], MD PGY-3 Obstetrics and Gynecology - Resident

Background

Delivery by Cesarean section (CS) is one of the most commonly performed surgeries in the world. Advantages of CS are well described, however it is a major surgery that presents complications including those involving the urinary system. Currently it is common practice to place an indwelling bladder catheter prior to CS. Although the current recommendation published in the ERAS guideline is to remove indwelling catheters immediately post operatively, it is typical that they are left in for upwards of 24 hours (1). Indwelling foley catheters are associated with higher rates of urinary tract infection (UTI), post-operative pain, and prolonged postoperative hospitalization (2). There is evidence to suggest that omitting the use of indwelling catheters during CS could reduce these risks which could significantly benefit patients in their post-partum recovery (3).

A Cochrane review completed in 2014 on this subject included only three randomized controlled trials comparing use versus non-use of indwelling bladder catheter in CS. UTI was significantly reduced in non-catheterized groups in both studies who assessed for bacteriuria (3,4). In one study, patient ambulation, first postoperative voiding time, and duration in hospital were all significantly less in the non-catheterized group, however this study had significant heterogeneity in their groups particularly involving regional versus general anesthetic (3). A common reason for routine bladder catheterization is the idea that it reduces bladder injury by increasing visualization of the lower uterine segment, however interestingly there were no bladder injuries described across evaluated studies in the non-catheterized groups (3,4,5). So far, limitations mainly in methodology and sample size in previous work have made it difficult to provide sound clinical recommendations when it comes to non-use of routine bladder catheterization. Our hope is to conduct a randomized controlled trial at the Foothills

Ethics ID: REB24-0044

Study Title: Use versus non-use of bladder catheterization in uncomplicated cesarean delivery

PI: [name]

Version 1.0 - January 23, 2024

Research Protocol

Medical Centre that focuses on sound methodology and clear outcomes to build on the existing evidence on this topic.

Primary Research Question

To investigate the impact of routine bladder catheterization in uncomplicated CS on hospitalization time (readiness to discharge), time to ambulation, urinary retention, development of UTI, prevention of bladder injury, operating time, and patient satisfaction.

Study Design

This would be a randomized controlled trial conducted on the labour and delivery and post-partum unit at a large academic site (Foothills Medical Centre) in Calgary, Alberta. Study recruitment of patients awaiting delivery via CS would occur either in participating prenatal clinics in Calgary or in obstetrical triage by a trained nurse research assistant. Participants would be randomized into either a catheterized or non-catheterized group prior to their scheduled elective CS. Allocation concealment will be ensured by using either a central computer generator for randomization if funding permits, otherwise sealed, opaque, and sequenced envelopes will be used. Since we anticipate potential differences in patients with increasing parity, randomization will be stratified by parity and blocked to prevent imbalance in treatment groups.

Patients placed in the catheterized group will have an indwelling catheter placed after anesthetic has been administered. It would be removed at 12 hours post CS by postpartum nursing staff. Participants in the non-catheterized group would be encouraged to empty their bladders just prior to transfer to the operating room where they will undergo surgery without an indwelling catheter. If there is an intraoperative decision to place an indwelling catheter, the reason for doing so will be recorded on the post-operative survey described below. Due to the nature of this study design, blinding of either party is not feasible. Inclusion criteria are women who are 18 years of age or older with a singleton pregnancy presenting for an elective primary or repeat CS. Exclusion criteria include diagnosis of abnormal placentation including placenta previa, vasa previa, or suspected invasive disease.

The primary outcome will be time at readiness for discharge post-surgery. Secondary outcomes will include time to ambulation, incidence of urinary retention, incidence of UTI requiring antibiotics in the first 4 weeks postpartum, incidence of bladder injury in surgery, operating time, and patient satisfaction as measured by the Maternal Satisfaction for Caesarean Section questionnaire (MSCS).

Urinary retention will be defined based on a patient's inability to spontaneously void requiring either - and-out catheterization or placement of an indwelling catheter during the postoperative course. The data for postoperative time at readiness for discharge as well as ambulation time will be collected via a form that will be distributed to the postpartum nursing team. It will be important to ensure that the time at clinical *readiness* for discharge be recorded, as there are many variables (such as waiting on prescriptions) that could act as confounders to the actual time to discharge. The operating surgeon will provide data on intraoperative observations and complications. This will be collected via an electronic post-operative questionnaire using free software such as Qualtrics. This will be used to identify

Ethics ID: REB24-0044

Study Title: Use versus non-use of bladder catheterization in uncomplicated cesarean delivery

PI: [name]

Version 1.0 - January 23, 2024

Research Protocol

intraoperative difficulties and complications such as bladder injury, bladder distension, difficulty with hysterotomy or bladder avoidance during surgery, and the clinical decision to place indwelling catheter either intraoperatively or immediately postoperatively. If the surgeon decides at any point during the surgery to place an indwelling catheter, intention to treat analysis will be upheld and those participants will be analyzed according to their original group.

The MSCS is a validated 22-item questionnaire developed initially as an efficient tool for evaluating maternal satisfaction in women undergoing CS under regional anesthesia (6). This will also include a visual analogue scale (VAS) for simple maternal satisfaction. This scale was recommended in a large comparative review published in BMC as a short option for patient satisfaction specific to maternity care with high reliability, and good construct validity. This will be completed by the patient prior to discharge

Statistical Analysis

The primary outcomes are hospitalization time, time to ambulation, urinary retention, development of UTI, prevention of bladder injury, and patient satisfaction. For many of these baseline estimates for a sample size calculation are not available. However, based on data from FMC the average length of stay post CS is 2.1 days. Converting this to hours and assuming a power of 80% and setting alpha at .05 a sample 30 subjects would provide 80% power to detect a 50% difference in length of stay. A sample of 128 would have adequate power to detect a difference in LOS of 25%. We aim to recruit 140 individuals. Currently FMC performs between 62-100 elective CS per month (2022-march 23 data). Therefore, with even a modest recruitment rate we should easily recruit sufficient patients. Time to discharge, time to ambulation and patient satisfaction (VAR) will be analysed with a comparison of means after appropriate transformations. A t-test will be used to assess statistical significance. Bivariate data such as urinary retention, UTI and bladder injury will be described as rates and statistical significance assessed with a Fisher's exact test.

Risks and Benefits

The benefits of the proposed study are the gathering of information that could help guide clinical practice with regards to the use of bladder catheterization in uncomplicated cesarean delivery. While evidence exists, there are significant issues with methodology that make the results difficult to interpret. Based on previous literature, the largest risk to participants is the need for intraoperative catheterization based on the surgeon's discretion after abdominal entry. Precaution to maintain a sterile environment in this case would be taken.

Ethics ID: REB24-0044

Study Title: Use versus non-use of bladder catheterization in uncomplicated cesarean delivery

PI: [name]

Version 1.0 - January 23, 2024

Research Protocol

References

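### The protocol names one primary outcome in Study Design and six in Statistical Analysis, with one alpha of .05 and no multiplicity rule

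*Combined protocol and SAP*

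**What the plan says.** The protocol describes the status of its outcomes in three places.

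- **Primary Research Question** lists seven outcomes together, without ranking them.
- **Study Design** (outcomes paragraph) ranks them: "The primary outcome will be time at readiness for discharge post-surgery". It continues: "Secondary outcomes will include time to ambulation, incidence of urinary retention, incidence of UTI requiring antibiotics in the first 4 weeks postpartum", followed by bladder injury, operating time and satisfaction.
- **Statistical Analysis** opens: "The primary outcomes are hospitalization time, time to ambulation, urinary retention, development of UTI, prevention of bladder injury, and patient satisfaction". Operating time is not in this list.

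Statistical Analysis then assigns t-tests to time to discharge, time to ambulation and satisfaction, and Fisher's exact tests to urinary retention, UTI and bladder injury. The level is given once, in the sample-size text: "assuming a power of 80% and setting alpha at .05". That text concerns length of stay only: "a sample 30 subjects would provide 80% power to detect a 50% difference in length of stay" and "A sample of 128 would have adequate power to detect a difference in LOS of 25" per cent. The target is stated as "We aim to recruit 140 individuals". No multiplicity adjustment, testing order, all-must-succeed rule or other criterion for a positive trial appears anywhere.

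**The concern.** The primary outcome fixes what the alpha applies to, what the sample size is for, and what the conclusion rests on. Here two sections of the same version give different answers. An analyst following Study Design tests one outcome at .05 and treats the rest as supporting. An analyst following Statistical Analysis has six outcomes of equal standing and no rule for combining them.

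The trial is unblinded and is meant to inform practice. If the choice is left until results are known, whichever of the six is significant can be reported as the primary finding, and .05 is then not the trial's false-positive rate. If the six were properly controlled instead, the 80% power in the sample-size text would no longer hold.

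**Working it through.** **1. The two outcome lists side by side**

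| Outcome | Study Design | Statistical Analysis | Test named |
|---|---|---|---|
| Readiness for discharge / hospitalization time | primary | primary | t-test |
| Time to ambulation | secondary | primary | t-test |
| Satisfaction | secondary | primary | t-test |
| Urinary retention | secondary | primary | Fisher |
| UTI | secondary | primary | Fisher |
| Bladder injury | secondary | primary | Fisher |
| Operating time | secondary | not listed | none |

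Five outcomes change status and one drops out.

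**2. The plan's own sample size**

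Input from Statistical Analysis: "based on data from FMC the average length of stay post CS is 2.1 days". So the mean is 2.1 × 24 = 50.4 h, a 25% difference is 12.6 h and a 50% difference is 25.2 h. No SD, sidedness or allocation ratio is stated. I assume two-sided tests and 1:1 allocation, and solve for the SD.

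- With 64 per arm, 80% power and alpha 0.05, the t-test implies an SD of about 25.2 h, so d = 12.6/25.2 = 0.5.
- Check by normal approximation: n per arm = 2(1.960 + 0.842)²/0.5² = 62.8, rounded up to 63, so N = 126. The t-test gives N = 128, as stated.
- At the same SD a 50% difference has d = 1.0 and needs N = 32 (normal) or 34 (t-test), against the stated 30. The figure of 30 implies a slightly smaller SD, 23.8 h by t-test.
- At N = 140 (70 per arm) and d = 0.5, power at alpha 0.05 is 83.6%.

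The stated power is therefore for one test at the full 0.05.

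**3. False-positive rate if any of six counts**

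- Six independent tests, each of true size 0.05: 1 − 0.95⁶ = 0.265. The upper bound is 6 × 0.05 = 0.30.
- Fisher's exact test is conservative for rare events. At 70 per arm its actual size is 0.0253 at a 10% event rate, 0.0135 at 5%, and practically 0 at 0.5%. These rates are assumptions; the protocol gives none.
- Three independent t-tests: 1 − 0.95³ = 0.1426. Combined with the three Fisher tests: 1 − 0.8574 × 0.9747 × 0.9865 × 1.000 = 0.176.
- With the three continuous outcomes correlated at 0.3 and 0.5, simulation gives about 0.170 and 0.159.
- With all six outcomes correlated at the same assumed event rates, the figure is about 0.15 at correlation 0.5 and 0.13 at 0.8.

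**4. Power if the six are controlled by Bonferroni**

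Each test is at 0.05/6 = 0.00833. At d = 0.5 the normal approximation gives n per arm = 2(2.638 + 0.842)²/0.5² = 96.9, rounded up to 97, so N = 194. The t-test gives 198. At N = 128, power falls from 80% to 56%. At N = 140, for a 12.6 h difference:

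| Assumed SD (h) | Power at 0.05 | Power at 0.00833 |
|---|---|---|
| 20 | 96% | 85% |
| 23.8 (implied by 30) | 88% | 68% |
| 25.2 (implied by 128) | 84% | 61% |
| 30 | 69% | 43% |

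**The case against.** The strongest reply is that one primary outcome is plainly intended. Study Design names one, labels the others secondary, and explains why readiness must be recorded with care. The sample size is built on length of stay alone. The six-item list resembles the one under Primary Research Question and may have been carried over loosely. This is probably right about intention, and it makes the repair easy. It does not remove the contradiction, because the only analysis text explicitly calls all six primary.

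Two further points stand as limits on the claim. First, .05 is written only in the length-of-stay calculation; applying it to all six tests is inference, though no other level is offered. Second, the protocol does not state an any-of-six rule; it only fails to exclude one. If all six had to succeed, alpha would not be inflated. But power could then be no higher than that of the weakest test, which for an event as rare as bladder injury would be very low, so the stated 80% would fail on that reading too.

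Finally, 26.5% is the independence figure and should not be quoted as the realistic one, and every power figure depends on an SD that the protocol does not give. Both points are accepted, and ranges are shown for that reason.

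**Conclusion.** The concern holds and must be fixed before analysis. The one-versus-six contradiction and the absence of any multiplicity or success rule are in the current text and need no assumptions.

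The size of the consequence does depend on assumptions. If any of six counts, family-wise error is about 16-18% with the assumed event rates of 10%, 5% and 0.5% and correlation of 0 to 0.5 among the continuous outcomes. It drops to about 13% if all six are strongly correlated, still more than twice the nominal 5%. If Bonferroni is applied, power at 140 participants is 61% at the implied SD, and 43% to 85% for SDs of 30 down to 20 h.

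**What to change.** Replace the opening sentence of Statistical Analysis with text that follows Study Design, for example:

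> The single primary outcome is time from surgery to readiness for discharge, tested two-sided at 0.05. Time to ambulation, urinary retention, UTI, bladder injury, operating time and satisfaction are secondary. They are reported with 95% confidence intervals and do not on their own support a claim of efficacy.

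The last clause is a reporting choice rather than part of the contradiction, but it settles how a significant secondary result may be used.

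In the same edit:

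- Rank the outcomes under Primary Research Question in the same way.
- Use one definition of the primary outcome throughout. Study Design separates readiness from actual discharge, while Statistical Analysis speaks of hospitalization time and length of stay.
- Name an analysis for operating time.

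This needs a few sentences and no extra patients. Alpha stays at 0.05, and 140 participants give about 84% power for a 12.6 h difference at the implied SD. The one cost is that a significant secondary result can no longer be presented as primary success.

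If the sponsor does want six primary outcomes, the protocol must specify a multiplicity procedure and a new sample size. Under Bonferroni, length of stay alone would need about 198 participants for 80% power at the implied SD.

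### Statistical Analysis lists six primary outcomes where Study Design names one, and plans only a significance test although 140 women would leave a null primary result uncertain by about 8 h either way

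*Combined protocol and SAP*

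**What the plan says.** - **Primary outcome, Study Design:** "The primary outcome will be time at readiness for discharge post-surgery". Time to ambulation, urinary retention, UTI, bladder injury, operating time and satisfaction are listed there as secondary.
- **Primary outcomes, Statistical Analysis:** the opening sentence gives six: hospitalization time, time to ambulation, urinary retention, UTI, bladder injury and satisfaction. No allowance for multiple testing is described.
- **Sample size, Statistical Analysis:** "based on data from FMC the average length of stay post CS is 2.1 days". From this, with alpha .05, "a sample 30 subjects would provide 80% power to detect a 50% difference in length of stay", and then "A sample of 128 would have adequate power to detect a difference in LOS of 25" per cent. The recruitment aim is 140. The section gives no SD, does not say whether the test is one- or two-sided, and does not explain why 25% was chosen.
- **Analysis, Statistical Analysis:** means are to be compared, after transformation where appropriate, for time to discharge, time to ambulation and satisfaction. "A t-test will be used to assess statistical significance". Binary outcomes are to be described as rates and tested with Fisher's exact test. No confidence interval, margin or smallest important difference is mentioned.

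**The concern.** Two gaps combine. First, the two sections disagree on what is primary. With six primary outcomes, each tested at .05, a positive trial could be declared on any one of them. With one, it could not.

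Second, the only inferential result planned for the primary outcome is a p-value. The sizing takes a large difference, a quarter of the stay, as its target. If the true difference is smaller, a non-significant result is quite likely, and a p-value does not show which differences have been ruled out. The Background says that earlier trials could not support firm recommendations, partly because of their size. A null result reported without an interval could be taken as evidence that the catheter makes no difference to recovery time when the data do not show that.

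**Working it through.** **Inputs from the protocol (Statistical Analysis).** Mean stay 2.1 days; alpha .05; 30 subjects for 80% power at a 50% difference; 128 subjects for adequate power at 25%; 140 to be recruited.

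**Assumptions.** Two-sided test; 1:1 allocation (70 + 70); 30 and 128 read as totals; noncentral t power. Reading 30 as per arm does not fit the plan: the SD would be 34.3 h and 128 women would have only 54% power for 25%.

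**Step 1: differences in hours.** 2.1 × 24 = 50.4 h. 50% is 25.2 h; 25% is 12.6 h.

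**Step 2: the SD implied by the plan.**
- From the 30-subject sentence: 15 per arm has 80% power at a standardised difference of 1.060, so SD = 25.2 / 1.060 = 23.8 h.
- From the 128 sentence, if adequate means 80%: 64 per arm has 80% power at 0.499, so SD = 12.6 / 0.499 = 25.2 h.

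**Step 3: do the plan's own figures hold?** At SD 23.8 h, 128 women have 84.5% power for 12.6 h and 140 have 87.6%. At SD 25.2 h, 140 have about 83%, and 30 subjects have about 75% for the 50% difference. The two sentences therefore agree approximately, and the 25% claim stands at either SD.

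**Step 4: what 140 women can detect.** With 70 per arm, 80% power needs a standardised difference of 0.477.
- SD 23.8 h: 0.477 × 23.78 = 11.3 h.
- SD 25.2 h: 0.477 × 25.25 = 12.0 h.

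**Step 5: expected precision.** Half-width of the 95% interval = t(.975, 138) × SD × √(2/70) = 1.977 × SD × 0.169.
- SD 23.8 h: 7.95 h, about 8.0 h.
- SD 25.2 h: 8.4 h.

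A result is non-significant when the observed difference is smaller than the half-width. With a half-width of 8 h, an observed difference of zero gives limits of −8 and +8 h. An observed difference just short of 8 h gives limits from about 0 to about 16 h.

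**Step 6: sensitivity, using an illustrative 6 h difference.** The 6 h is not a figure in the protocol, and SDs of 20 and 15 h are assumed values.

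| SD (h) | Power for 6 h, 140 women | Difference with 80% power |
|---|---|---|
| 25.2 | 29% | 12.0 h |
| 23.8 | 32% | 11.3 h |
| 20 | 42% | 9.5 h |
| 15 | 65% | 7.2 h |

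On a log scale (log-normal, mean 50.4 h, raw SD 23.8 h, so log-SD .448), 80% power is reached at 9.7 h, and power for 6 h is 38%.

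**Step 7: six tests.** If six true null hypotheses were tested independently at exactly .05, the chance of at least one false positive would be 1 − 0.95^6 = 26%. This is only a guide: the outcomes are related, and Fisher's test on rare events rejects less often than 5%.

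**The case against.** The strongest reply is that the plan misses no figure that it states. The calculation holds for 25%, and choosing that target is a design judgement. This stands, and it is why no larger sample is requested.

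A reader might go further and infer that the target is unattainable. The catheter "It would be removed at 12 hours post CS by postpartum nursing staff", and 12.6 h exceeds 12 h. The Background adds that in usual practice "it is typical that they are left in for upwards of 24 hours", so the contrast tested here is smaller. The one trial cited for shorter stay is reported without a figure and with a caution: "duration in hospital were all significantly less in the non-catheterized group, however this study had significant heterogeneity in their groups". The documents do not support that inference:
- Twelve hours is not a ceiling on delay. The Background names UTI and pain as consequences of catheters, and either could outlast the catheter.
- The arms are not wholly separated by those 12 h. The retention definition allows a catheter to be placed later in the postoperative course, and catheters may be placed during surgery in the non-catheterized group.
- The 0.6 h excess is immaterial: at SD 23.8 h, 140 women have 84% power for 12 h.

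It may also be said that power for smaller differences cannot be known. That is right. The SD is back-solved, 6 h is an illustration, and the planned transformation may do better than raw hours. The SD also describes actual stay, while the primary outcome is readiness, chosen to leave out delays such as waiting for prescriptions; its SD could be smaller. These points limit how firmly low power can be asserted. They do not supply the missing interval or resolve the conflict over primary outcomes.

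Finally, the plan does compare means, so it would be unfair to say that it plans no estimate. What it omits is the uncertainty around that estimate.

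**Conclusion.** The point holds in a limited form. The contradiction between one and six primary outcomes is plain in the text and needs no assumption. The reporting gap is also in the text: a significance test is specified and no interval is.

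The size of that gap rests on the back-solved SD, a two-sided test, 1:1 allocation, all 140 women analysed and raw hours. On those terms the interval is about 8.0 to 8.4 h either side, and 80% power is reached only at about 11.3 to 12.0 h. A smaller SD or a log-scale analysis would improve this. Power for 6 h runs from about 29% to 65% over the SDs shown, so no single figure should be quoted as the trial's power for a smaller effect.

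The documents do not show that the trial is wrongly sized, that 12.6 h is impossible or that more women are needed. The catheter removal time is not questioned. What follows is narrower: a non-significant t-test on its own could not be reported as no effect.

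**What to change.** Three changes to Statistical Analysis:

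1. **One primary outcome.** Name time at readiness for discharge as the single primary outcome, matching Study Design, and move the other five to secondary.
2. **Estimate with interval.** Replace the significance-only sentence with, for example: *The between-group difference in time to readiness for discharge will be reported with its 95% confidence interval. A non-significant result will not be reported as no effect if the interval includes a difference of [value set by the investigators before recruitment].* If the analysis is on a transformed scale, state the scale on which the interval and that value will be expressed.
3. **Sizing statement.** Give the SD from the hospital's length-of-stay data and the difference that 140 women detect with 80% power at that SD, with the sidedness of the test. Say that length of stay is a proxy for readiness. The 23.8 h and 25.2 h used here are back-solved and should not be copied in as if observed.

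The cost is protocol wording, one SD taken from data the site has already drawn on for its mean stay, and one confidence interval. No extra women and no change to treatment are needed.

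### Randomization is stratified by parity, but the t-test planned for the continuous outcomes ignores parity, so its standard error is too large to the extent that parity predicts the outcome

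*Combined protocol and SAP*

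**What the plan says.** On allocation, the Study Design section states: "Since we anticipate potential differences in patients with increasing parity, randomization will be stratified by parity and blocked to prevent imbalance in treatment groups". It gives neither the parity categories nor the block size.

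The same section names the primary outcome: "The primary outcome will be time at readiness for discharge post-surgery".

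On analysis, the Statistical Analysis section states: "Time to discharge, time to ambulation and patient satisfaction (VAR) will be analysed with a comparison of means after appropriate transformations". It continues: "A t-test will be used to assess statistical significance". Binary outcomes go to Fisher's exact test.

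No covariate, stratified test or regression model appears anywhere in the document. The mention of transformations concerns the scale of the outcome and does not bring parity into the comparison.

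**The concern.** Design and analysis do not match. Blocking within parity strata forces the arms to have nearly the same parity mix, so outcome differences between parity groups hardly contribute to the difference in means. The true sampling variance of that difference is therefore smaller than under simple randomization. The two-sample t-test does not know this. Its pooled variance still contains the between-parity component, so it overstates the standard error whenever parity predicts the outcome.

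What is at stake is calibration and efficiency, not validity. P-values would be somewhat too large, and a 95% interval derived from the t-test somewhat too wide. The argument concerns the t-test only; this standard-error reasoning does not carry over to Fisher's test.

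**Working it through.** **Inputs from the protocol (Statistical Analysis).** Mean post-cesarean stay 2.1 days = 50.4 h. A 25% difference is 12.6 h (N = 128) and a 50% difference is 25.2 h (N = 30). Power is 80%, alpha 0.05, planned N 140.

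**Assumptions.** Two-sided alpha and 1:1 allocation (neither is stated). The outcome SD and parity's R² are not given.

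**The plan's own figure.** Without an SD, 128 cannot be reproduced from the stated inputs alone. Solving the t-based sample-size formula backwards gives an SD of about 25.2 h for N = 128. Putting that back in:

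- Normal formula: n per arm = 2 × (1.96 + 0.842)² × (25.2/12.6)² = 62.8, so 63 per arm, total 126. The t-based formula gives 128.
- The same SD for the 50% difference gives 32 (normal) or 34 (t) against the stated 30. Solving from N = 30 instead gives an SD of about 23.8 h.

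The two SDs are close but not equal, so both are carried below.

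**Figures that depend on R² alone.** Let k = √(1−R²), with R² on the analysed scale.

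- Ratio of the t-test SE to the true SE = 1/k
- True type I error of the t-test = 2 × [1 − Φ(1.96/k)]
- Coverage of its nominal 95% interval = 1 − true type I error

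| R² | SE ratio | Type I error | Coverage |
|---|---|---|---|
| 0 | 1.000 | 5.0% | 95.0% |
| 0.01 | 1.005 | 4.9% | 95.1% |
| 0.02 | 1.010 | 4.8% | 95.2% |
| 0.05 | 1.026 | 4.4% | 95.6% |
| 0.10 | 1.054 | 3.9% | 96.1% |
| 0.20 | 1.118 | 2.8% | 97.2% |

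**Hours and power at N = 140, raw-hours scale, SD 25.2 h.** SE = 25.2 × √(4/140) = 4.26 h, and z = 12.6/4.26 = 2.958.

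- Half-width: t-test 1.96 × 4.26 = 8.35 h; adjusted 8.35 × k
- Power: t-test Φ((z − 1.96)/k); adjusted Φ(z/k − 1.96)
- Equivalent N: the size at which the t-test, after the same stratified randomization, reaches the adjusted model's power at 140

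| R² | Adjusted half-width | Power, t-test | Power, adjusted | Equivalent N |
|---|---|---|---|---|
| 0.05 | 8.14 h | 84.7% | 85.9% | 144.7 |
| 0.10 | 7.92 h | 85.4% | 87.7% | 149.7 |
| 0.20 | 7.47 h | 86.8% | 91.1% | 160.3 |

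At R² = 0 both analyses have 84.1% power. With the SD solved from N = 30, power is 88.6 / 89.2 / 90.5% for the t-test and 89.5 / 91.1 / 93.9% adjusted.

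**Simulation check.** N = 140, SD 25.2 h, permuted blocks of 4, two strata (40/60), 40,000 trials per cell; t-test against adjusted model:

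- R² = 0.05: type I error 0.045 vs 0.050; power 0.843 vs 0.855
- R² = 0.10: type I error 0.040 vs 0.050; power 0.849 vs 0.874
- R² = 0.20: type I error 0.027 vs 0.048; power 0.861 vs 0.907
- R² = 0: power 0.835 vs 0.835

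Three strata (30/45/25) give nearly the same results.

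**Is stratification the cause?** With three strata (35/45/20), R² = 0.20, no treatment effect and 10,000 trials each: under stratified blocks the t-test's average SE was 4.25 h, the actual SE 3.83 h and the type I error 0.027. Without stratification the figures were 4.25 h, 4.24 h and 0.051. The t-test is correctly calibrated under simple randomization. The excess comes from stratifying and then ignoring the strata.

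**The case against.** The strongest reply is that the error is on the safe side and small. The t-test is conservative, and its power rises slightly with R² (84.1% at 0, 86.8% at 0.20), so the planned analysis does no worse than planned. The loss is only relative to a better alternative: 1.2 power points at R² = 0.05 and 2.3 at 0.10. A simple conservative test is defensible in a small single-centre trial. This stands, and it limits the weight of the point.

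The size also rests on an assumed R². The protocol says only "Since we anticipate potential differences in patients with increasing parity", without naming an outcome, and its stated purpose is to avoid imbalance. If parity explains 1% or 2% of the variance, the gain is 0.2 or 0.5 power points. This too stands: the mechanism is certain, the magnitude is not.

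The plan promises no confidence interval, so the remark on width applies to the interval that would accompany the t-test. The same standard error drives the p-value, which is planned. The hour and power figures depend on back-solved SDs and a normal approximation that runs about 0.3 to 0.7 points above the simulation, and they need not survive a transformation. The SE and type I figures do not depend on the SD.

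None of this favours leaving parity out. If parity proves irrelevant, adjustment costs next to nothing. Adding it later is weaker than specifying it now: the trial is unblinded, and a covariate chosen after outcomes are known is open to challenge.

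**Conclusion.** The point holds as a conditional matter of efficiency and calibration. The planned t-test ignores the one factor on which randomization is stratified. Its standard error is overstated by about 2.6% to 11.8% for R² between 0.05 and 0.20, by 1% or less for R² up to 0.02, and not at all at R² = 0. On the raw-hours scale with SD 25.2 h, adjustment would be worth about 5, 10 or 20 participants at R² of 0.05, 0.10 or 0.20. The sample size does not need to change. The correction is advisable rather than essential, and it makes the primary analysis agree with the randomization.

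**What to change.** - In Study Design, state the number of parity strata and their cut-points.
- In Statistical Analysis, replace the t-test for time to discharge, time to ambulation and satisfaction with a linear model on the planned scale (transformed if needed), with arm and the parity strata used at randomization as terms.
- Report the adjusted difference between arms with a 95% confidence interval. If the outcome is transformed, say how the result will be back-transformed (after a log, as a ratio of geometric means).
- Fisher's exact test can stay for bladder injury. A parity-stratified comparison for urinary retention and UTI is optional where event counts allow, and does not follow from the argument above.

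The cost is a few sentences of text and one degree of freedom per stratum beyond the first. Parity must be recorded in any case in order to randomize, so no new data are needed.
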